**Restoration of Spectral Resolution with Hearing-aid Amplification**

**NCT03850678**

**Study Protocol and Analysis Plan**

**March 13, 2019**

## **Brief Summary**

The objective of this study protocol is to determine the efficacy of using aided measures of spectral resolution to set the dynamic range of hearing with hearing-aid amplification. Measures of spectral resolution will be obtained, as will measures of speech recognition.

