## **Significance/Purpose:**

Adults with hearing loss are more vulnerable to interference from background noise than adults with normal hearing. Despite the fact that the ability to extract speech information imbedded in background noise requires decoding differences in level across frequency (spectral information), few studies have addressed the extent to which we can provide spectral information to listeners with hearing loss. This fundamental gap in our knowledge prevents us from effectively addressing the systemic effects of hearing loss on communication, income, and ability to socialize with others. This work is a new application of established methods of characterizing spectral resolution to that of the most common device for rehabilitation of hearing loss—hearing-aid amplification. The proposed experiments will examine the degree to which access to spectral information can be restored to adults with hearing loss and the feasibility of utilizing this information to decrease interference from background noise. Aim 1 will delineate the impact of hearing-aid amplification on spectral decoding. Technology options that must be set by the clinician or hearing-aid manufacturer will be examined, including the frequency-specific gain, compressor speed, and number of compression channels. The proposed experiments will test the hypothesis that restoration of the lost dynamic range of hearing can support the encoding of spectral information. It is also hypothesized that the combination of technology options that best restore access to spectral information will differ across individuals and that these differences across individuals can be partially accounted for by an estimate of outer hair cell function. Aim 2 will determine the extent to which restoring access to spectral information supports speech recognition in background noise, under the guiding hypothesis that improving spectral resolution increases speech understanding. If it can be demonstrated that measures of spectral resolution with the provision of amplification are useful at delineating those who stand to benefit from different technology options, the knowledge gained could then be applied to the clinic to allow for clinicians to more successfully choose among different rehabilitation options.

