**Statistical Analysis:**

We plan to enroll 20 subjects with normal hearing and 40 subjects with sensorineural hearing loss (per experiment). While we plan to recruit the same subjects for each experiment, additional subjects will be recruited as needed. Additional subjects will be recruited for pilot testing and to account for attrition. We expect an effect size of 0.37 ( $np2$ ) or greater. Using G\*Power (v3.1) we estimated sample sizes necessary to detect an effect size of over 0.23 (power = 80%,  $\alpha = 0.05$ ). For Aim 1, planned comparisons to examine the effect of prescriptive procedure, compression speed, and number of compression channels on the sharpness of tuning measured will be conducted using an ANOVA or, if we find that the assumptions of the ANOVA to be violated, a linear mixed effect model. For Aim 2, planned comparisons to examine the effect of dynamic range of hearing (small, large) and tuning status (poor tuning, sharp tuning) on proportion correct will be conducted using an ANOVA or, if we find that the assumptions of the ANOVA to be violated, a linear mixed effect model. While results are not expected to differ by sex, differences by sex will be analyzed for all experiments. Other variables, such as age, degree of hearing loss, and working memory likely play a role in spectral resolution and speech recognition and will be considered as variables in our statistical models.

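### The objective claims efficacy for using the aided measure to set dynamic range, but no planned contrast compares a measure-guided setting with a common one

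*Combined protocol and SAP*

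**What the plan says.** The Brief Summary of the combined protocol and SAP gives a single objective, to "determine the efficacy of using aided measures of spectral resolution to set the dynamic range of hearing with hearing-aid amplification".

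Statistical Analysis lists the planned comparisons:

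- **Aim 1:** the "effect of prescriptive procedure, compression speed, and number of compression channels on the sharpness of tuning measured".
- **Aim 2:** "planned comparisons to examine the effect of dynamic range of hearing (small, large) and tuning status (poor tuning, sharp tuning) on proportion correct".

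Neither entry names an interaction, a setting chosen from the measure, or a setting chosen without it. The description of fitting (Section 2 of the data collection procedures) gives no rule for choosing a setting from the Section 3 threshold.

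Significance/Purpose is narrower than the Brief Summary. It speaks of "the feasibility of utilizing this information to decrease interference from background noise", places Aim 2 "under the guiding hypothesis that improving spectral resolution increases speech understanding", and says that if the measures prove "useful at delineating those who stand to benefit from different technology options", then "the knowledge gained could then be applied to the clinic".

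**The concern.** To ask whether it is efficacious to use a measure to set something is to ask about a strategy. The quantity of interest is the outcome when the measure picks the setting, minus the outcome when everyone receives one setting picked without it. Individual selection can pay only if the best setting differs between listeners. Significance/Purpose hypothesises that it does differ for access to spectral information, but the named comparisons on speech are factor effects, and an average effect does not test this.

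What is at stake is the headline conclusion. A significant Aim 2 effect, set beside the objective as worded, could be reported as efficacy of measure-guided setting when the analysis had shown only that sharper tuning, or one of the two dynamic ranges, goes with better speech scores.

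**Working it through.** **Aim 1.** Its outcome is the spectral measure itself. It can show which settings sharpen tuning, but not whether choosing by tuning improves speech.

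**Aim 2.** The plan does not say whether tuning status classifies listeners or settings, so both readings are followed.

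*Reading A: tuning status classifies listeners, and each listener is tested at both dynamic ranges.* Let D_P and D_S be the mean large-minus-small difference in proportion correct among listeners with poor and sharp tuning, and let p be the share with poor tuning. For the algebra only, suppose the rule gives large to the sharp group and small to the poor group; the opposite rule exchanges the roles.

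- The tuning main effect compares people and says nothing about choosing a setting.
- The dynamic-range main effect averages D_P and D_S. If it is positive, it favours large for everyone, which needs no measure.
- Interaction = D_S − D_P.
- Guided minus large-for-all = −p × D_P.
- Guided minus small-for-all = (1 − p) × D_S.

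Guided setting beats both common settings only if D_P < 0 and D_S > 0. If both are positive, both main effects and the interaction can be significant while large-for-all is still the better choice. The contrast can be formed from these cells, but it is not the same as a main effect, and the interaction alone does not settle it.

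*Reading B: tuning status classifies settings within a listener.* With Y the proportion correct,

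Y(sharp) − Y(poor) = [Y(sharp) − Y(common)] + [Y(common) − Y(poor)].

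Only the first bracket is the gain from using the measure. Both levels of the factor are defined by the measure, so neither is the unguided comparator. If the common setting is already every listener's sharpest, the first bracket is zero and the whole contrast comes from the second.

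**The plan's own sample size.** Inputs from Statistical Analysis: 40 hearing-loss subjects, effect size 0.23 (metric not stated), 80% power, alpha 0.05. Read 0.23 as Cohen's f, and assume one two-level within-subject factor with correlation 0.5:

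- λ = f² × N × m / (1 − ρ) = 0.0529 × 40 × 2 / 0.5 = 8.464, on 1 and 39 degrees of freedom.
- Power is 0.810, and 40 is the smallest N that reaches 80%.
- The implied standardised paired difference is √(8.464 / 40) = 0.46.

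The match depends on those assumptions. With correlation 0 the N is 77. With two independent groups it is 151 in total. Reading 0.23 as partial eta squared gives 9 within subjects or 29 between.

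**Power for the missing contrast.** For a paired t-test, two-sided alpha 0.05, 40 listeners, 80% power is reached at a standardised paired difference dz of 0.454. The documents give no expected gain from guiding, so the range is shown:

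| dz | N for 80% power |
|---|---|
| 0.3 | 90 |
| 0.4 | 52 |
| 0.5 | 34 |
| 0.6 | 24 |

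Listeners whose selected setting is the common one contribute a difference of zero if that condition is scored once. This pulls the mean gain down and should be allowed for.

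**The case against.** The strongest reply is that Aim 2 already contains what is needed. Dynamic range is a factor alongside tuning status. Under reading A, large-for-all or small-for-all is a common setting, and assignment by tuning status is a guided one. A two-factor ANOVA would ordinarily include the interaction. This stands to the extent that a reader might infer that no comparator exists under any definition of tuning status, and the documents do not support so strong a claim. What remains is that Statistical Analysis names neither the interaction nor the contrast, and does not say that dynamic range is varied within listeners.

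A second reply is that the working aims are in Significance/Purpose, which speaks of feasibility and mechanism, and the planned analyses address those. That is correct. The mismatch is with the objective in the Brief Summary, and rewording would cure it. A reader might also infer that the document intends to go from a tuning effect straight to clinical use. It does not: clinical use is conditional on showing that the measures identify who benefits.

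Finally, a reader might want a figure for how far sharp versus poor overstates the gain from guiding. If settings vary independently and normally within a listener (SD s) and the common setting sits at the listener's average, best-minus-worst is 2.06s with 4 settings and best-minus-common is 1.03s; with 8 settings they are 2.85s and 1.42s. The ratio of about two follows from symmetry, the assumptions come from outside the documents, and the calculation does not apply under reading A. It is an illustration, not evidence about this study.

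**Conclusion.** The concern holds as a mismatch between the stated objective and the named comparisons. Main effects of dynamic range or tuning status cannot by themselves support a conclusion that using the aided measure to set the dynamic range is efficacious. They can support the feasibility and mechanism aims. Under reading A the needed contrast is available but unplanned, so the rule and the common setting could be chosen after the speech scores are seen. Under reading B the unguided comparator is missing.

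The size of any overstatement cannot be derived from the documents. Its limiting case can: if one setting is best for everyone, guiding gains nothing over that setting, whatever the main effects show. Data collection is not invalidated. The conclusion does not depend on the sample-size reproduction, and it rests on Statistical Analysis being the full list of planned comparisons.

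**What to change.** State whether tuning status classifies listeners or settings, and whether dynamic range is varied within listeners. Then do one of the following.

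1. **Keep the efficacy objective.** In Aim 2, pre-specify one within-listener contrast in the hearing-loss group: proportion correct at the setting selected from Section 3 data only, minus proportion correct at one common tested setting fixed in advance. If tuning status classifies listeners, pre-specify the dynamic range by tuning status interaction together with the guided-minus-common contrast of the same cells. Fix the selection rule before speech scores are seen, explain why the common setting is the one listeners would get without the measure, and base the efficacy conclusion on this contrast. State that 40 listeners give 80% power only for a standardised paired difference of about 0.45 or more.
2. **Otherwise, restate the Brief Summary objective** as the association between aided spectral resolution and speech recognition.

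The first option costs one planned contrast and at most one extra speech condition per hearing-loss listener, or none if the common setting is already tested. Its limitation is low power for small gains: a standardised paired difference of 0.3 would need 90 listeners. The second option costs only wording, but gives up the efficacy claim.

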## **Significance/Purpose:**

Adults with hearing loss are more vulnerable to interference from background noise than adults with normal hearing. Despite the fact that the ability to extract speech information imbedded in background noise requires decoding differences in level across frequency (spectral information), few studies have addressed the extent to which we can provide spectral information to listeners with hearing loss. This fundamental gap in our knowledge prevents us from effectively addressing the systemic effects of hearing loss on communication, income, and ability to socialize with others. This work is a new application of established methods of characterizing spectral resolution to that of the most common device for rehabilitation of hearing loss—hearing-aid amplification. The proposed experiments will examine the degree to which access to spectral information can be restored to adults with hearing loss and the feasibility of utilizing this information to decrease interference from background noise. Aim 1 will delineate the impact of hearing-aid amplification on spectral decoding. Technology options that must be set by the clinician or hearing-aid manufacturer will be examined, including the frequency-specific gain, compressor speed, and number of compression channels. The proposed experiments will test the hypothesis that restoration of the lost dynamic range of hearing can support the encoding of spectral information. It is also hypothesized that the combination of technology options that best restore access to spectral information will differ across individuals and that these differences across individuals can be partially accounted for by an estimate of outer hair cell function. Aim 2 will determine the extent to which restoring access to spectral information supports speech recognition in background noise, under the guiding hypothesis that improving spectral resolution increases speech understanding. If it can be demonstrated that measures of spectral resolution with the provision of amplification are useful at delineating those who stand to benefit from different technology options, the knowledge gained could then be applied to the clinic to allow for clinicians to more successfully choose among different rehabilitation options.

## **Study Design**

### ***Data Collection Procedures:***

This study can be divided into 4 sections. For all four sections, the subject will sit in a sound attenuated booth.

### *Section 1 - Questionnaire and cognitive impairment screen*

At this time, each subject will complete a questionnaire that asks relevant questions about their medical and developmental history and educational level. Participants will be screened for a potential cognitive impairment using the Montreal Cognitive Assessment Basic (MOCA-B). The MOCA-B is a 10-minute cognitive screening tool to detect mild cognitive impairment. Participants are asked to perform tasks including connecting numbers and patterns on a sheet of paper, recalling words, naming of items, and simple math calculations. Participants with a score less than 26 will be informed of the test results and counseled to consult with their primary care physician. A screening for potential cognitive impairment is being implemented to limit the possible influence (i.e. confound) of cognitive impairment on our perceptual results.

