#### ***Test Time:***

The audiological test and hearing aid fitting is anticipated to take 1 hour to complete. Section two is anticipated to take approximately 3 hours and section three approximately 2 hours. Participants with NH require less time; they are not fit with hearing aids and undergo fewer conditions. In addition to hearing status, the duration will depend on how quickly each subject completes the study and on whether a current audiological test can be used, thereby saving time. Consequently, we anticipate the study will take approximately 3-6

hours per subject. Generally subjects complete the study in 2-3 sessions scheduled over the course of a couple weeks.

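### Does the missing analysis rule for low MoCA-B scores, and the unnamed working-memory measure, call for a change to the plan?

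*Combined protocol and SAP*

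**What the plan says.** Section 1 (Questionnaire and cognitive impairment screen) gives the MoCA-B a scientific purpose, to "limit the possible influence (i.e. confound) of cognitive impairment on our perceptual results". The action it attaches to the cut-off is a participant-care step: "Participants with a score less than 26 will be informed of the test results and counseled to consult with their primary care physician".

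The Statistical Analysis section sets the numbers per experiment: "We plan to enroll 20 subjects with normal hearing and 40 subjects with sensorineural hearing loss". It provides for extra enrolment in two places. One sentence allows more recruitment where the same listeners cannot be carried across experiments. The next reads: "Additional subjects will be recruited for pilot testing and to account for attrition". The MoCA-B score does not appear in that section. Working memory does, in an open-ended list with age and degree of hearing loss, as something to be considered in the models.

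Data Collection Procedures states: "This study can be divided into 4 sections". Those four sections describe a questionnaire, the MoCA-B, an audiogram, tympanometry, a fitting, detection of acoustic change and speech recognition. None is identified as a working-memory measure.

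**The concern.** A screen reduces confounding only if its result changes who is analysed or how. Here the result leads only to information and advice, so the stated purpose has no stated mechanism. Three matters look open: whether a listener below 26 is analysed, whether an excluded listener is replaced, and whether 20 and 40 count listeners before or after the screen.

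Two things could be at stake. Exclusion without replacement would shrink the hearing-loss group and reduce power. An analyst who settled the rule after seeing results could choose between two analysis sets, which raises the false-positive rate even if cognition has no effect.

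The working-memory point is separate: a model variable with no named instrument might turn out not to have been collected.

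**Working it through.** **1. Is a planned contrast biased?** The Test Time section says of normal-hearing listeners that "they are not fit with hearing aids and undergo fewer conditions", which implies that each listener is tested under several conditions. On that reading the Aim 1 comparisons (prescription, compressor speed, number of channels) are made within a listener, and a stable trait such as cognitive status cancels from the difference. No between-listener contrast has been shown to be affected either.

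**2. The plan's own sample size.** The document says "we estimated sample sizes necessary to detect an effect size of over 0.23", with 80% power and alpha 0.05. It does not give the test family, number of conditions, correlation or scale of 0.23, so 20 + 40 cannot be uniquely reproduced. The only effect size whose scale is labelled is the expected 0.37, given as partial eta squared.

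**3. Power if low scorers were dropped and not replaced.** The share below 26 is not given. I assume 5, 10, 20 or 40% of 40, which is 2, 4, 8 or 16 listeners and leaves 38, 36, 32 or 24. The test is a within-listener F test with 1 and n − 1 degrees of freedom, alpha 0.05.

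For a partial eta squared e, the noncentrality is λ = e/(1 − e) × (n − 1). At n = 40, e = 0.37 gives 0.37/0.63 × 39 = 22.9, and e = 0.23 gives 0.23/0.77 × 39 = 11.6.

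For Cohen's f with two levels and correlation ρ, λ = f² × n × 2/(1 − ρ). At n = 40, f = 0.23 and ρ = 0.5, this is 0.0529 × 40 × 2/0.5 = 8.46.

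| Analysed n | Partial eta² 0.37 | Partial eta² 0.23 | f = 0.23, ρ = 0.5 |
|---|---|---|---|
| 40 | 0.997 | 0.914 | 0.810 |
| 38 | 0.995 | 0.899 | 0.789 |
| 36 | 0.993 | 0.882 | 0.765 |
| 32 | 0.985 | 0.838 | 0.713 |
| 24 | 0.940 | 0.709 | 0.579 |

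In the middle column power is 0.812 at 30 listeners and 0.797 at 29, so 10 of the 40 could be lost before power fell below 80%. In the last column 40 is the smallest n that reaches 80% (39 gives 0.799), but only at ρ = 0.5. At ρ = 0.7 power is 0.956 with 40 and 0.902 with 32. At ρ = 0.3 it is 0.669 with all 40, so the target is missed whatever the screen does.

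**4. Power if low scorers were replaced.** The analysed count stays at 40. Enrolment is n/(1 − share) rounded up: 43, 45, 50 or 67 at 5, 10, 20 or 40%. The recruitment wording sets no ceiling.

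**5. Choosing the analysis set after results.** I simulated 40 within-listener differences with no true effect and low scorers no different from the rest. A two-sided one-sample t-test was run on all 40 and on those at 26 or above, with 400,000 repetitions, counting a positive if either p-value fell below 0.05. The error rate is about 6.0% with 2 low scorers, 6.5% with 4, 7.1% with 8 and 8.0% with 16.

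**6. Working memory.** The four section descriptions are summaries and not a full test list. The Significance/Purpose section relies on an estimate of outer hair cell function, and those sections do not describe a measure of that either. The text therefore supports only that the instrument is not named. Session times cannot show whether a test was planned. The Test Time section gives 1 hour to the audiological test and fitting and then says "Section two is anticipated to take approximately 3 hours and section three approximately 2 hours". In the procedures, however, Section 2 is the audiological test and fitting, and no time is given for Section 4. The labels do not line up, so a total of the hours proves nothing.

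**The case for a change.** The best case for a change is that it would be cheap. One sentence could fix the role of scores below 26 before results are seen, and another could name the working-memory test or delete the term. Recruitment partly through organisations for older people makes low scores likely enough to plan for. Exclusion is the ordinary reading of a screen, but it is not written down, and the provision for attrition does not say that a low score counts as attrition. Under the Cohen's f reading with two levels and correlation 0.5, 40 leaves no slack.

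The textual points stand: no rule is written and no instrument is named. The consequences are weaker. The no-slack result needs three assumptions that the document does not make, and the power losses also need exclusion without replacement, which the document nowhere proposes. The 8.0% error rate needs 40% of listeners below 26 and an analyst who reports whichever result is significant. The plan leaves wider choices open, such as ANOVA or mixed model and which covariates enter, so this one adds little. A missing working-memory score need not be lost for good, since listeners attend over 2–3 sessions, the same people are sought for each experiment, and a later visit could supply it.

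**Conclusion.** The concern does not call for a change. The document leaves out a detail that an analyst would fill sensibly. Followed as written, low scorers are counselled and stay in the analysis. On the usual reading of a screen, they are excluded and replaced through the open recruitment. Neither course gives a wrong or biased result for the planned contrasts, and nothing shows one to be better than the other.

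The size is small. At the effect the plan expects, power is at least 0.94 even if 16 of 40 are lost and none replaced. At 0.23 read as partial eta squared, it holds at 0.80 or more down to 30 listeners. Choosing the analysis set after results costs about 1.0 to 1.5 percentage points of error at an assumed 5–10% of low scorers. These figures rest on within-listener contrasts with one numerator degree of freedom, and on assumed shares below 26. If 0.23 is Cohen's f, the result turns on an unstated correlation, which is a question about the sample-size statement and not about the screen.

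The unnamed working-memory measure is likewise a matter of description. The term sits in an illustrative list of variables to be considered, and no planned comparison depends on it.
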